10. The planned times for admission, discharge, as well as start and end of the collection intervals for urine and faeces are approximate. The procedures are to be performed within a time window of ± 4 h to the planned time.
11. Subjects are to collect faeces at home within 24 h intervals before being admitted to trial site for once-weekly in-house collection intervals. Home collection intervals: Day 15-16, 22-23, 29-30. If faeces are collected in the subsequent in-house collection interval, the faeces previously collected at home will be discarded. If no faeces are collected in the subsequent in-house collection interval (no defaecation) at the trial site, the faeces collected at home will be used instead for analysis.
12. For definition of the individual subject's end of trial see Section [6.2.3](#)
13. Drug and alcohol screening will be done at this time point.
14. Based on specific instructions provided, subjects will collect a pre-dose faeces sample at home in specific containers provided by the clinical trial site approximately 48 h before trial drug administration.
15. Confirmation of fitness includes physical examination, vital signs, ECG, recordings of AEs and concomitant therapies as well as evaluation of safety laboratory assessed on Day 8.
16. At this time point, only a sample for haematocrit measurement is taken.
17. PCR testing for SARS-CoV-2 will be performed at admission on Day – 1, Day 2 and at each admission to the trial site for the 24-h visits. Polymerase chain reaction testing for SARS-CoV-2 will be performed as needed based on the current status of the pandemic. SARS-CoV-2 testing on Day 2 may take place at any time during this day.
18. Metabolite profiling sampling times may be adapted based on information obtained during trial conduct (e.g., levels of radioactivity in each urine and/or plasma sample) as long as the overall blood volume stays the same.

FLOW CHART 2A (MICROTRACER HUMAN ADME)*

Visit	Day	Planned time (relative to first drug administration [h:min])	Approximate clock time of actual day [h:min]	Event and comment	Safety laboratory	Blood sampling for PK and total radioactivity ^{2,9}	PK ⁵ urine	PK ⁴ faeces	Blood sampling for metabolic profiling ¹⁸	12-lead ECG	Vital signs (BP, PR)	Questioning for AEs and concomitant therapy
1	-21 to -2			Screening (SCR) ¹	A ¹³			X ¹⁴		X	X	
2	-1	-18:00	14:00	Admission to trial site	B ^{13,17}		X ³					X
	1	-2:00	06:00			X ³			X ³	X ³	X ³	↑

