7. STATISTICAL METHODS AND DETERMINATION OF SAMPLE SIZE

7.1 NULL AND ALTERNATIVE HYPOTHESES

No confirmatory analysis will be conducted for this study. Data will be reported with descriptive statistics only.

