Safety laboratory data, vital signs and PK parameters will be analysed (based on cohorts) with clear differentiation between baseline and on-treatment measurements. Measurements will be considered on-treatment, if they were taken within the on-treatment phase as defined in [Table 6.1: 1](#).

More details on the technical implementation of these analyses are provided in the ADS Plan of this TSAP.

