7.8.2 Laboratory data

The analyses of laboratory data will be descriptive in nature and will be based on BI standards (8).

Analyses will be based on normalised values, which means transforming to a standard unit and a standard reference range. The original values will be analysed if the transformation into standard unit is not possible for a parameter.

Descriptive statistics of laboratory values over time and for the difference from baseline (see [Section 6.7](#)) will be provided. Frequency tables of changes between baseline and last value on treatment with respect to the reference range will be presented.

Unscheduled measurements of laboratory data will be assumed to be repeat measurements of the most recent scheduled measurement (e.g. for follow-up or confirmation of a particular value). Therefore, unscheduled measurements will be assigned to the planned time point of the previous scheduled measurement. Descriptive statistics will be calculated by planned time point based on the worst value of the subject at that planned time point (or assigned to that planned time point).

Clinically significant abnormal laboratory values are only those identified either in the Investigator's comments or at the Report Planning Meeting at the latest. It is the Investigator's responsibility to decide whether a lab value is clinically significant abnormal or not.

Laboratory data will be compared to their reference ranges. Values outside the reference range will be highlighted in the listings.

Clinically relevant findings in laboratory data will be reported as baseline conditions (prior to administration of study drug) or as AEs (after administration of study drug) if judged clinically relevant by the investigator, and will be analysed as such.

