7.8.3 Vital signs

Only descriptive statistics are planned for this section of the report. Descriptive statistics of vital signs over time and for the difference from baseline (see [Section 6.7](#)) will be provided.

Unscheduled measurements of vital signs will be assigned to planned time points in the same way as described above for laboratory data. However, for vital signs, descriptive statistics will be calculated by planned time point based on the last value of the subject at that planned time

point (or assigned to that planned time point). If the time of measurement is missing for a scheduled measurement, the scheduled measurement will be used in calculation of descriptive statistics (as time difference between scheduled and unscheduled cannot be assessed).

If the time of measurement is missing for an unscheduled measurement, this measurement will be listed but will be ignored for the calculation of descriptive statistics.

Clinically relevant findings in vital signs data will be reported as baseline conditions (prior to first administration of study treatment) or as AEs (after first administration of study treatment) if judged clinically relevant by the investigator, and will be analysed as such.

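### The SAP's rule for unscheduled laboratory and vital-sign values has no stop at drug administration, so post-dose values can be summarised in the pre-dose row

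*SAP*

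**What the plan says.** SAP 7.8.2 starts from a premise: "Unscheduled measurements of laboratory data will be assumed to be repeat measurements of the most recent scheduled measurement". It concludes that "unscheduled measurements will be assigned to the planned time point of the previous scheduled measurement", and the summary for each planned time point is then "based on the worst value of the subject at that planned time point", counting values assigned to it.

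SAP 7.8.3 carries this over: "Unscheduled measurements of vital signs will be assigned to planned time points in the same way as described above for laboratory data". The difference is that the last value is used instead of the worst. An unscheduled vital sign without a recorded time is listed but left out of the statistics.

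Three other places bear on the same values:

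- SAP 6.1 says laboratory data and vital signs will be analysed "with clear differentiation between baseline and on-treatment measurements", and it treats a measurement as on-treatment according to when it was taken, starting at drug administration.
- Protocol 7.2.5 assigns measurements by the actual treatment at the time of measurement. SAP section 4 states that the SAP agrees with the protocol's methods.
- SAP 6.7 sets baseline as the latest value obtained before dosing.

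**The concern.** Treating an unscheduled sample as a repeat of the latest scheduled one is reasonable when scheduled samples are close together. Here the gap around dosing is long for laboratory tests, and the rule is silent about dosing.

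The protocol itself foresees samples that are not repeats. Section 5.2.6.1.4 tells the investigator to obtain liver tests, unscheduled if necessary, when symptoms suggest hepatic injury and no results are available. Taken between dosing and Day 8, such a test is a new post-dose observation, yet 7.8.2 would file it under Day -1.

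At stake is the correctness of the by-time-point laboratory and vital-sign tables. A pre-dose row could contain post-dose values, while the post-dose rows would lack them.

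**Working it through.** The plan gives no figure to reproduce: "Data will be reported with descriptive statistics only". The check is to apply 7.8.2 and 7.8.3 literally to the schedule.

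**Scheduled times (Flow Charts 1, 2A and 2B; hours from dosing)**

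- Set B laboratory tests, all cohorts: -18 (Day -1), 168 (Day 8), then end of study.
- Haematocrit, cohorts 1 and 2a: -18, 1.5, 8, 24, 168. At the three intermediate times the footnote reads "At this time point, only a sample for haematocrit measurement is taken".
- Haematocrit, cohort 2b: -18, 168. Flow Chart 2B marks the laboratory column on Day 2, but with the metabolite-profiling footnote. I did not count that mark as a set B or haematocrit sample.
- Vital signs, all cohorts: -2, 1.5, 4, 12, 24, 216.

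**Post-dose window that maps to the pre-dose time point**

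The window runs from dosing to the first scheduled post-dose time. Its share of the in-house post-dose period is that time divided by 216 h.

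| Parameter | Cohorts | Window | Share |
|---|---|---|---|
| Set B except haematocrit | all | 0 to 168 h | 168/216 = 78% |
| Haematocrit | 1, 2a | 0 to 1.5 h | 1.5/216 = 0.7% |
| Haematocrit | 2b | 0 to 168 h | 78% |
| Vital signs | all | 0 to 1.5 h | 0.7% |

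These limits are nominal. With the 10% window for safety assessments in protocol 6.1, 1.5 h becomes 1.35 to 1.65 h, and 168 h becomes 151.2 to 184.8 h.

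**Illustration (assumed values, not from the documents)**

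- Laboratory: one subject has ALT 25 U/L on Day -1 and an unscheduled 150 U/L on Day 3. Under 7.8.2 the Day -1 entry is the worse value, 150. The baseline under 6.7 stays 25. A change from baseline computed for the Day -1 row would be 150 - 25 = +125 for that subject. The Day -1 mean rises by 125/8 = 15.6 U/L in a cohort of 8, and by 125/16 = 7.8 U/L in the pooled microtracer cohorts. The Day 8 row is unchanged.
- Vital signs: a systolic reading 30 mmHg below the pre-dose value at 1 h, if it is the last reading before 1.5 h, lowers the pre-dose mean by 30/8 = 3.75 mmHg.

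**The texts side by side**

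For the same Day 3 sample, SAP 6.1 and protocol 7.2.5 go by the actual sampling time, which is post-dose. SAP 7.8.2 places it at a pre-dose planned time point. The SAP does not say which prevails.

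**The case against.** The strongest reply is that SAP 6.1 governs: the data are first split at dosing by actual time, and 7.8.2 then assigns repeats within each side. SAP 6.1 also leaves technical implementation to the ADS Plan, and 7.8.2 refers to company laboratory standards; neither is among the documents. The programming may already contain a guard. This stands as a reason not to assert that the tables will be wrong. It does not make the text right, because 7.8.2 is explicit, has no exception, and leaves an early post-dose value with no post-dose row to go to.

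A reader might also infer that the rule hides an acute safety effect. The documents do not support that. Individual values are listed, and laboratory values outside the reference range are highlighted. Findings judged clinically relevant become adverse events, and hepatic alerts have their own table as events of special interest. Baseline under 6.7 is not contaminated. The table of baseline against last on-treatment value does not depend on the assignment rule, although it would not show an excursion that a later sample had already resolved.

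Nor does the problem reach every unscheduled value. Untimed vital signs are not summarised, and a laboratory value counts only if it is the worst. Vital signs taken between 24 h and 216 h go to the 24 h row. That blurs their timing over 192 h, but it does not cross dosing.

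**Conclusion.** Wrong as written; minor in severity. Sections 7.8.2 and 7.8.3 lack a guard at drug administration and so conflict with SAP 6.1 and protocol 7.2.5. The exposed window is 168 h for set B analytes in all cohorts, except haematocrit in cohorts 1 and 2a, where it is 1.5 h. For vital signs it is 1.5 h.

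Only the by-time-point descriptive statistics are affected, including a possible non-zero change from baseline in a pre-dose row. Baseline, the shift table, listings, adverse event reporting and the pharmacokinetic endpoints are not.

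The conclusion assumes that 7.8.2 and 7.8.3 are followed as worded and that such samples occur; the documents give no count. The length of the on-treatment phase is redacted. If it ended before 168 h, a later value would be follow-up rather than on-treatment, but still not pre-dose.

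**What to change.** Add to SAP 7.8.2 and 7.8.3:

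- An unscheduled value taken after drug administration is never assigned to a pre-dose planned time point.
- One taken before the first scheduled post-dose time point for that parameter is summarised in a separate row, either unscheduled on-treatment or worst on-treatment. The SAP should name which.

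Keep the worst-value rule for laboratory data and the last-value rule for vital signs otherwise. Replacing them with scheduled-only statistics would be a preference, and this problem does not require it. If the ADS Plan already has such a guard, the SAP should state it so that the documents agree.

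The cost is a few lines of SAP text and minor programming for the extra row. No data collection changes.

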7.8.3 Vital signs

Only descriptive statistics are planned for this section of the report. Descriptive statistics of vital signs over time and for the difference from baseline (see [Section 6.7](#)) will be provided.

Unscheduled measurements of vital signs will be assigned to planned time points in the same way as described above for laboratory data. However, for vital signs, descriptive statistics will be calculated by planned time point based on the last value of the subject at that planned time

point (or assigned to that planned time point). If the time of measurement is missing for a scheduled measurement, the scheduled measurement will be used in calculation of descriptive statistics (as time difference between scheduled and unscheduled cannot be assessed).

If the time of measurement is missing for an unscheduled measurement, this measurement will be listed but will be ignored for the calculation of descriptive statistics.

Clinically relevant findings in vital signs data will be reported as baseline conditions (prior to first administration of study treatment) or as AEs (after first administration of study treatment) if judged clinically relevant by the investigator, and will be analysed as such.

7.8.4 ECG

Abnormal findings in ECG will be reported as baseline conditions (at screening) or as AEs (during the trial) if judged clinically relevant by the investigator, and will be analysed as such. No separate listing or analysis of ECG data will be prepared.

7.9 OTHER ANALYSIS

7.9.1 Physical examination

Physical examination findings will be reported as relevant medical history/baseline condition (if a condition already exists before first administration of study treatment) or as AE (if condition emerges after first administration of study treatment) and will be summarised as such. No separate listing or analysis of physical examination findings will be prepared.

7.9.2 Body weight

[figure not shown]
Body weight will only be listed.

8. TIMEPOINT OF RELEASE OF TREATMENT INFORMATION

The treatment information will be loaded into the trial database as requested during study conduct.

11. HISTORY TABLE

Table 11: 1 History table

Version	Date (DD-MMM-YY)	Author	Sections changed	Brief description of change
1.0	08-Dec-23		None	This is the final TSAP.
